## **Confidentiality Statement**

Data and information contained in this document are considered to constitute trade secrets and confidential commercial information, and the legal protections provided to such trade secrets and confidential information are hereby claimed under the provisions of applicable law. No part of this document may be publicly disclosed without the written consent of Philip Morris Products S.A.

Confidential

P1-CMS-01-US

Final 2.0 Amendment 1.0, 22-May-2017

Page 70 of 106

Related to PMI\_RD\_WKI\_000759

The following details will be recorded for AEs:

- Description of event/symptom
- Onset date and time of event
- End date and time of event
- Severity/intensity rated as follows:

Mild: Awareness of symptoms but easily tolerated, no disruption of normal activities.

Moderate: Discomfort enough to cause interference with usual activity.

Severe: Incapacitating with inability to work or do usual activity.

- Any other action taken (such as concomitant medication, non-drug therapy, both, or none)
- Outcome of AE noted as follows:
  - Fatal
  - Not recovered/not resolved
  - Recovered/resolved
  - Recovered/resolved with sequelae
  - Recovering/resolving
  - Unknown

# 8.2.2 Period of Collection

Starting from the time when consent was obtained, the PI or designee will record all adverse events observed, queried, or spontaneously reported by the study participants. An adverse event query will be performed as scheduled as per Principal Investigator or designee's direction at the screening visit and throughout the confinement period and prior to being released from

**Clinical Study Protocol** 

Confidential

P1-CMS-01-US

Final 2.0 Amendment 1.0, 22-May-2017

Page 71 of 106

Related to PMI\_RD\_WKI\_000759 CSP

confinement. Study participants will be asked non-leading questions such as "How do you feel now?", "How have you felt since last asked?", or "Have you taken any medication since last asked?" If the presence of any symptom(s), adverse event(s), and/or concomitant medication is recorded, the clinical staff may advise the study participants to remain at the clinic site for safety reasons until the Principal Investigator or designee decides it is safe for the study participants to leave. If the study participant decides to leave despite the advice of the Principal Investigator or designee, he/she will be asked to sign a waiver.

Any non-serious AE that is ongoing during the Safety Follow-Up Period will be actively followed-up by the Principal Investigator or designee during that period until it has been resolved, stabilized (i.e., no worsening of the condition), or an acceptable explanation has been found (e.g., a chronic condition).

At the end of the Safety Follow-Up Period, all ongoing non-serious AEs will be documented as "ongoing" and no follow-up information will be sought for on them anymore by the Principal Investigator or designee. At that point, the Investigator will assess whether the subject should be referred to his/her General Practicioner to have their ongoing AEs addressed accordingly.

All SAEs will be followed up by the Investigator or designee, despite their continuation after the end of the Safety Follow-Up Period, until their resolution, stabilization (i.e., no worsening of the condition), or an acceptable explanation has been found (e.g., a chronic condition).

## 8.2.3 Intensity of Adverse Event

- Mild: Awareness of symptoms but easily tolerated, no disruption of normal activities.
- Moderate: Discomfort enough to cause interference with usual activity.
- Severe: Incapacitating with inability to work or do usual activity.

Change in severity (intensity) needs to be documented.

## 8.2.4 Relationship to Study Procedures

This study will not involve administration of any investigational product and therefore, the Principal Investigator or designee will make a determination of the relationship of the AE to study procedures (not related, related) according to the following guidelines:

Related:	This relationship suggests a probable temporal sequence of the event with study procedure(s) exists. Based upon the Principal Investigator, the association of the event with the study procedure(s) seems probable and the event is unlikely to be attributed to concurrent diseases or other drugs or chemicals.
	This relationship suggests a reasonable temporal sequence of the event with study procedure(s) exists. Based upon the Principal Investigator's clinical experience, the association of the event seems possible.
Not Related:	The event has been judged by the Investigator to have no relationship to study procedure(s).

# 8.3 Reporting of Serious Adverse Events

Any SAE observed during the period of collection by any of the parties involved in this study (including the Investigational site personnel) must be reported by that party within 24 hours of first awareness to the sponsor representative. The Sponsor representative will be notified in writing (SAE report form) within 24 hours of when a SAE is first recognized or reported by contacting:

#### **Confidentiality Statement**

P1-CMS-01-US

Final 2.0 Amendment 1.0, 22-May-2017

Page 73 of 106

Related to PMI\_RD\_WKI\_000759

Sponsor representative contacts:

Company: United BioSource Corporation (UBC) Pharmacovigilance Fax: Email:

Subsequently, a summary of the SAE will be sent to the sponsor representative within three working days of the original notification.

The IRB will be notified in writing (*e.g.*, facsimile) within 24 hours (1 working day) of when a reportable SAE is first recognized or reported. In addition, a copy of the written confirmation or summary of the SAE, as submitted to the sponsor representative, will also be submitted to the IRB within 3 working days of when the reportable SAE is first recognized or reported. The IRB's serious and unexpected adverse experience submission form will be completed and submitted with the copy of the written confirmation or summary of the SAE.

As further information regarding an already reported SAE becomes available to any of the parties involved in this study, such follow-up information should be reported to the sponsor representative and if applicable to the IRB, according to the same timelines described above.

# 8.4 Adverse Events Leading to Discontinuation

Study participants will be advised they are free to withdraw from the study at any time. Over the course of the study, the Investigator and/or the Sponsor may discontinue participation of any study participant from the study in the case of unnecessary risk, adverse events, or noncompliance. When a study participant withdraws or is discontinued from the study, all safety data normally required at the end of the study will be obtained, if possible.

Subjects who are discontinued from the study because of an AE will undergo the early termination procedures as soon as practical after the day of discontinuation and will enter the period of safety follow-up. Any AEs or SAEs that are ongoing at the end of the Safety Follow-up Period will be managed as described in section 8.2.2.

If, in the opinion of the Investigator, Sponsor, or the IRB, the incidence and severity of AE(s) outweighs the benefit of continuing the study, the study may be terminated. In the event this course of action is to be pursued, the Investigator will make every attempt to communicate

## **Confidentiality Statement**

Data and information contained in this document are considered to constitute trade secrets and confidential commercial information, and the legal protections provided to such trade secrets and confidential information are hereby claimed under the provisions of applicable law. No part of this document may be publicly disclosed without the written consent of Philip Morris Products S.A.

CSP

Related to PMI\_RD\_WKI\_000759

with the Sponsor prior to the decision to develop a complete plan of action and to assess outcomes.

# 8.5 **Reporting of Other Events Critical to Safety Evaluations**

## 8.5.1 Abnormal Results of Laboratory Tests

Any clinical safety laboratory test result that is outside of the normal reference range will be reviewed by the Investigator and assessed for clinical significance according to its severity. The severity of abnormal laboratory test result must be assessed using CTCAE 4.03 grading scales. Whenever that grading scheme is not available for the laboratory result of concern, the Investigator should assess the severity and the clinical significance of that result using his/her medical judgment.

Abnormal laboratory test results detected **at the screening visit** whose CTCAE grades are 2 or higher or still are CTCAE grade 1 and deemed clinically significant are usually concomitant disease or a manifestation of one and must be recorded accordingly. However, in some instances, they may be assessed as AEs (and therefore must be handled according to the directions in section 8.2) or as manifestations of already reported AEs. This decision will require a careful assessment of the abnormal result within the clinical context on a case-by-case basis and will depend on the Investigator's medical judgment.

Abnormal laboratory test results detected **after the screening visit** whose CTCAE grades are 2 or higher or still are CTCAE grade 1 and deemed clinically significant must be either recorded as AEs (and handled according to the directions in section 8.2) or linked to a concomitant disease or still to an already reported AE.

The principles for assessing and reporting abnormal laboratory test results, emerging after the screening visit, using CTCAE 4.03 grading scales are set up in Table 2:

Table 3Principles for assessing and reporting abnormal laboratory test results

Grading	Clinically significant?	Is it a grade increase from previous results in study? §	Report?
---------	----------------------------	---	---------

## **Confidentiality Statement**

Philip Morris Products SA

Confidential

P1-CMS-01-US

Final 2.0 Amendment 1.0, 22-May-2017

Page 75 of 106

Related to PMI RD WKI 000759 CSP

Grade 1	No	Not applicable	No
Grade 1	Yes	No	No*
Grade 1	Yes	Yes	Yes, as AE or linked to an already reported AE
Grade 2 or higher	No/Yes	No	No*
Grade 2 or higher	No/Yes	Yes	Yes, as AE or linked to an already reported AE

\* in this situation, this abnormal lab test result is either a manifestation of a concomitant disease or of an already reported AE.

§ grade increase in this context means the value is higher than the one from the screening visit.

Any other abnormal clinical laboratory result (including those that are not part of the core safety assessments) can, at the discretion of the Investigator, be reviewed and assessed. Even if they do not meet the criteria of the CTCAE grading scheme, the Investigator may consider them to be of clinical significance and, if they are, must report them as AEs.

In general, laboratory values will be recorded as "increased <lab parameter>" or "decreased <lab parameter>" to ensure consistency of recording/coding.

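### The Table 3 footnote defines a grade increase by the laboratory value, not the grade; read literally, it contradicts its own column and the text of Protocol section 8.5.1

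*Protocol*

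**What the plan says.** Protocol section 8.5.1 sets the scale: "The severity of abnormal laboratory test result must be assessed using CTCAE 4.03 grading scales". For results after screening, its prose covers those "whose CTCAE grades are 2 or higher or still are CTCAE grade 1 and deemed clinically significant must be either recorded as AEs"; the alternative is to link the result to a concomitant disease or to an AE already on record. The prose mentions neither the direction of change nor a change in grade.

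Table 3 then sets out the reporting principles. For clinically significant grade 1 results, and for all results of grade 2 or higher, the outcome depends on one column: "Is it a grade increase from previous results in study". If the answer is yes, the outcome is "Yes, as AE or linked to an already reported AE". If it is no, the outcome is No*, with the note that "in this situation, this abnormal lab test result is either a manifestation of a concomitant disease or of an already reported AE". A grade 1 result that is not clinically significant is never reported.

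Footnote § is the only definition of the deciding column: "grade increase in this context means the value is higher than the one from the screening visit".

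Three other places bear on the point:
- The naming convention after Table 3, which begins "In general, laboratory values will be recorded as", provides terms for decreased as well as increased parameters.
- Protocol section 7.2 makes worsening of a pre-existing condition after Visit 1 an AE.
- SAP section 5.5.4.2 summarizes each laboratory parameter over time with normal and abnormal counts. AE counts by group go to Tables A 11 and A 12.

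**The concern.** Grade measures severity, while a laboratory value has a direction. When a parameter worsens by falling, its grade goes up and its value goes down. A footnote that tests the value therefore gives the wrong answer to the column's question for low-side changes. On the high side it answers yes to any rise, even one that leaves the grade unchanged.

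Hematology, clinical chemistry and urine analysis are listed under the secondary safety objective, and AEs are reported by group. Two site staff could read section 8.5.1 in good faith and classify the same discharge result differently, one from the prose and one from the table.

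**Working it through.** No figure in the plan is at issue, so the check traces Table 3 under two readings of footnote § and compares each with the prose.

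**Inputs.** The rows of Table 3, footnote §, the No* note and the post-screening prose, all in Protocol section 8.5.1. The documents do not reproduce the CTCAE thresholds, so grades are kept abstract. A normal result is treated as below grade 1 (assumption).

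**Readings.** Literal: the answer is yes if the laboratory value is higher than at screening. Grade: the answer is yes if the grade is higher than at screening. CS means clinically significant.

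| Case | Screening to Visit 3 | Literal | Grade | Prose |
|---|---|---|---|---|
| 1 | Normal to low grade 2 | No* | Report | Record or link |
| 2 | Low grade 1 to low grade 3 | No* | Report | Record or link |
| 3 | Low, falls further within grade 1, CS | No* | No* | Record or link |
| 4 | High, rises within grade 2, not CS | Report | No* | Record or link |
| 5 | High, rises within grade 1, CS | Report | No* | Record or link |
| 6 | High, rises within grade 1, not CS | Not reported | Not reported | Not required |
| 7 | Low grade 3 improves to low grade 2 | Report | No* | Record or link |
| 8 | High grade 1 to high grade 2 | Report | Report | Record or link |

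The readings differ in five of the eight cases: 1, 2, 4, 5 and 7.

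- **Cases 1 and 2.** The literal reading puts a new or worsening low abnormality in the No* row. In case 1 the No* note fails as well: the participant was normal at screening, so there need be no concomitant disease or earlier AE to explain the result.
- **Cases 4 and 5.** The grade has not changed, yet the literal table calls this an increase. The yes rows allow an AE or a link to an earlier AE. They omit the link to a concomitant disease that the prose allows, although section 8.5.1 says that an abnormality of this kind at screening is usually recorded as one.
- **Case 7.** An improving result counts as an increase because the value rose.
- **Case 6.** A grade 1 rise that is not clinically significant stays out under both readings, which limits the over-reporting.
- **Case 3.** Both readings give No*, while the prose asks for recording or linking. Rewording the footnote alone does not settle this case.

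**Reach.** Appendix A schedules safety laboratory tests at Visit 1 and at discharge on Visit 3. That is one scheduled comparison per parameter per participant, or 14 × 1 = 14 per parameter and 7 per group. If a misclassified result would be a participant's only AE, it moves that group's AE percentage in Table A 11 by 1/7 = 14.3 percentage points. The documents give no basis for estimating how often this would happen.

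**The case against.** The strongest reply is that the value in the footnote can be read as the grade, because the column asks about a grade increase and the first column of the table is headed Grading. On that reading cases 1, 2, 4, 5 and 7 come out sensibly. This stands as a likely account of what was meant. It also supports rewording, since the footnote is the only definition that site staff have.

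A reader might infer that worsening low values go unreported in this study. The documents do not support that:
- The prose of section 8.5.1 is mandatory and covers both directions.
- Section 7.2 makes worsening an AE, and section 8.2 requires worsening to be evaluated and recorded.
- Terms for decreased parameters are provided.
- Every value still enters SAP Tables A 13 to A 15. Listing 15 shows the result, its range indicator, its clinical significance and any AE link.

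A reader might also infer that harmless rises in general are counted. Only results at grade 2 or higher, or clinically significant grade 1 results, can be affected. Of these, only a non-significant rise within grade 2 or higher fits that description.

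Nor can it be said that every parameter with a low-side grade is affected. Which parameters have one depends on CTCAE thresholds that are not in the documents.

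Finally, No* can be defended as a row for results already explained. That holds when the abnormality was present at the same grade before. It does not hold for case 1.

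**Conclusion.** The point holds as an internal contradiction in a safety-reporting rule. Taken literally, footnote § conflicts with its own column heading, with the post-screening prose of section 8.5.1, with section 7.2 on worsening, and with the provision for decreased terms. Following it as written would misclassify results in both directions, and the rest of the section neither adopts nor overrides it.

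The size is small. The effect is confined to whether a result is classed as an AE, and so to Tables A 11 and A 12. It concerns 14 participants judged to be in good health, with one scheduled draw after screening. The saccharin transit time analysis is untouched. The conclusion rests on the literal reading being one that a site could reasonably apply, and it needs no assumption about CTCAE cut-points. The footnote should be corrected, but the point does not threaten the study's main results.

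**What to change.** Reword footnote § so that it refers to the grade: *the CTCAE grade is higher than the grade at the screening visit, whether the value rose or fell.*

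That sentence does not finish the job. Two mismatches must be reconciled with it:

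- **Comparator.** The column heading compares with earlier results in the study, the footnote with screening only. The two differ only when there is a repeat or unscheduled result in between. Both should name the same comparator.
- **Condition.** The prose of section 8.5.1 has no grade-increase condition, and the table does (case 3). The section should say how the two fit together: for example, whether No* means linked to a documented concomitant disease or AE, and what happens when neither exists. The yes rows should also agree with the prose on whether a link to a concomitant disease is allowed.

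In the same edit, correct the lead-in sentence, which points to Table 2 although the table is numbered 3.

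The cost is one reworded sentence and short aligning edits. No new data are needed, because section 8.5.1 already requires out-of-range results to be assessed for severity.

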# **9** STUDY ACTIVITIES

# 9.1 Screening Visit (Day -30 to -1)

At Visit 1 (Screening Visit), study participants will undergo the procedures outlined in Appendix A to check eligibility criteria, including providing informed consent, undergoing a brief physical examination, nasal and throat exam, vital signs, skin prick test (SPT), spirometry testing, STT test, exhaled carbon monoxide (eCO) measurements, urine cotinine assessment, medical and smoking history and blood and urine collection for medical lab exams.

Following Visit 1, study participants who pass all of the inclusion criteria and do not present any of the exclusion criteria will be asked to return to the clinic for Visit 2.

# **9.2** Confinement Period (Day 1 to Day 2)

During Visit 2, selected inclusion and exclusion criteria will be reassessed to ensure study participants are still eligible for enrollment (Appendix B – Inclusion and Exclusion Criteria Assessment). All study participants will have baseline assessments performed (Appendix A), including STT test.

Study participants will be confined in the clinic from the beginning of Visit 2 until discharge at Visit 3. During this confinement period study participants will abstain from drinking any alcohol and any drinks containing caffeine. Standard meals will be served. Drug restrictions applicable to study participant exclusion will also be maintained until the end of the study.

No cigarettes are to be smoked from midnight ( $\pm 1$  hour) between Visit 2 and Visit 3 until 8 am on the day of Visit 3. On the day of Visit 3, at least 8 hours after last cigarette, CC smokers, who want to smoke, will have a cigarette at 8 am $\pm 30$  minutes and then have the STT test performed immediately after smoking (5-10 minutes post T0). T0 will be defined as the start of cigarette smoking for smokers. T0 should be the same for all smokers within an acceptable time window of 1 hour. Never smokers will also have the STT test performed in the morning at 8 am  $\pm 30$  minutes (designated T0 $\pm 30$  minutes). All study participants (smokers and never smokers) will then have the STT test performed at 4h (may be performed until 4h30 min), 8h (may be performed until 8h30 min), and 12h (may be performed until 12h30 min) post T0, ensuring at least approximately 4 hours between the beginning of each STT test. The

## **Confidentiality Statement**

Data and information contained in this document are considered to constitute trade secrets and confidential commercial information, and the legal protections provided to such trade secrets and confidential information are hereby claimed under the provisions of applicable law. No part of this document may be publicly disclosed without the written consent of Philip Morris Products S.A.

Philip Morris Products SA

Clinical Study Protocol

Confidential

P1-CMS-01-US

Final 2.0 Amendment 1.0, 22-May-2017

Page 77 of 106

Related to PMI\_RD\_WKI\_000759

participant will be asked to confirm he/she can no longer feel the sweet taste. Study participants will drink a glass of water (approximately 240 mL) before STT tests are performed.

Samples for plasma nicotine assessment will be collected at approximately the same time points that STT test is performed at  $T_0$ , 4h (may be performed until 4h30 min), 8h (may be performed until 8h30 min), and 12h (may be performed until 12h30 min) post  $T_0$ .

Nasal scraping of the inferior turbinate of both nostrils will be performed on all 14 study participants at the end of Visit 3, after all other clinic assessments, following the "Method establishment to obtain human nasal epithelial sample using the Rhino-probe".

Full procedure will be described in the "Method establishment to obtain human nasal epithelial sample using the Rhino-probe". Upon conclusion of all clinic assessments, at the time of Discharge on Visit 3, the Principal Investigator or designee will perform a brief physical examination on the study participant.

# **9.3** Safety Follow-Up Period

From the Discharge on Visit 3, the study participant will enter a 1-day Safety Follow-Up Period during which spontaneously reported new AEs/serious AE (SAE)s will be recorded, and the active follow-up of ongoing AEs/SAEs will be done by the site with a phone call to the study participant.

Any non-serious AE that is ongoing during the Safety Follow-Up Period will be actively followed-up by the Principal Investigator or designee during that period until it has been resolved, stabilized (i.e., no worsening of the condition), or an acceptable explanation has been found (e.g., a chronic condition).

At the end of the Safety Follow-Up Period, all ongoing non-serious AEs will be documented as "ongoing" and no follow-up information will be sought for on them anymore by the Principal Investigator or designee. At that point, the Investigator will assess whether the subject should be referred to his/her General Practicioner to have their ongoing AEs addressed accordingly.

All SAEs will be followed up by the Investigator or designee, despite their continuation after the end of the Safety Follow-Up Period, until their resolution, stabilization (i.e., no worsening of the condition), or an acceptable explanation has been found (e.g., a chronic condition).

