## 2.3.2 Anticipated Foreseeable Risks due to Study Procedures

The risk of procedures (*e.g.*, blood samples, nasal scrapes, spirometry) are deemed to be on par with procedures routinely performed during normal or extended health examinations by the study participant's health care professional. To monitor study participants for risks associated with study procedures after discharge, a follow-up period of 1 day is implemented.

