**Clinical Study Protocol** 

Confidential

P1-CMS-01-US

Final 2.0 Amendment 1.0, 22-May-2017

Page 41 of 106

Related to PMI\_RD\_WKI\_000759

test performed immediately after smoking (5-10 minutes post T0). T0 will be defined as the start of cigarette smoking for smokers (time point of first product use during study day). T0 should be the same for all smokers within an acceptable time window of 1 hour. Never smokers will also have the STT test performed in the morning at 8 am  $\pm$  30 minutes (designated T0 $\pm$  30 minutes). All study participants (smokers and never smokers) will then have the STT test performed until 4h30 min), 8h (may be performed until 8h30 min), and 12h (may be performed until 12h30 min) post T0, ensuring at least approximately 4 hours between the beginning of each STT test. The participant will be asked to confirm he can no longer feel the sweet taste. Study participants will drink a glass of water (approximately 240 mL) before STT tests are performed.

Samples for plasma nicotine assessment will be collected at approximately the same time points that STT test is performed at  $T_0$ , 4h (may be performed until 4h30 min), 8h (may be performed until 8h30 min), and 12h (may be performed until 12h30 min) post  $T_0$ .

Nasal scraping of the inferior turbinate of both nostrils will be performed on all 14 study participants at the end of Visit 3, after all other clinic assessments, except the brief physical examination which will be done after the nasal scraping:

- For 4 study participants, the nasal scraping (left nostril with method 1, right with method 2) will be performed and samples collected for subsequent histological assessment.
- For the 10 remaining study participants, 5 will undergo nasal scraping using method 1, and 5 using method 2. For all 10 study participants, cells from one nostril will be added into one buffer, cells from the other nostril into a second buffer. Samples will be collected for subsequent RNA quantity and quality analysis.

Full procedure is described in the "Method establishment to obtain human nasal epithelial sample using the Rhino-probe".

Upon conclusion of all clinic assessments, at the time of discharge on Visit 3, the Principal Investigator or designee will perform a brief physical examination on the study participant.

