From the discharge on Visit 3, the study participant will enter a 1-day Safety Follow-Up Period during which spontaneously reported new AEs/serious AEs (SAEs) will be recorded, and the active follow-up of ongoing AEs/SAEs will be done by the site.

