## 8.2.1 Collection of Information

Any non-serious AE occurrence during the study must be documented in the subject's medical records in accordance with the Principal Investigator's normal clinical practice and on the AE page of the CRF. SAEs that occur during the study must be documented in the subject's medical record, on the AE CRF, and on the SAE form.

AEs should be collected mainly via face-to-face interview with the subject through spontaneous reporting or by the use of consistent, open, non-directive questions from the PI(s) or designee(s) (e.g., "Have you had any health problems since you were last asked? or "How have you been feeling since you were last asked?"). Information recorded will include: verbatim description of the AE/SAE, start and stop dates, seriousness, severity (intensity), action taken (e.g., whether or not the AE/SAE led to the subject's discontinuation from the study), and outcome (e.g., resolved, stabilized). Information to be recorded about a SAE should also include, whenever possible, onset and resolution dates and times, circumstances leading up to the event, clinical elements such as clinical course, specific vital signs and test results that may explain the pathophysiology of the event, as well as alternative explanations to its occurrence.

Whenever a medically meaningful diagnosis is available to comprise a set of reported signs and/or symptoms, it should be preferentially provided as the AE or SAE term, rather than the individual signs and/or symptoms. Otherwise, each one of those signs and/or symptoms should be reported separately as event terms.

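### The 1-day follow-up is meant to monitor procedure risks after discharge, but a participant who leaves without an AE has no solicited contact during it

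*Protocol*

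**What the plan says.** Protocol Section 2.3.2 names nasal scrapes among the study procedures that carry risk and gives the purpose of the follow-up: "To monitor study participants for risks associated with study procedures after discharge, a follow-up period of 1 day is implemented".

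Section 4.1 places the scraping: "Nasal scraping of the inferior turbinate of both nostrils will be performed on all 14 study participants at the end of Visit 3". It follows all other clinic assessments, and only the brief physical examination is stated to come after it.

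For the period after discharge, Section 9.3 has two rules. New events fall in a period "during which spontaneously reported new AEs/serious AE (SAE)s will be recorded". For existing events, "the active follow-up of ongoing AEs/SAEs will be done by the site with a phone call to the study participant". Section 4.1 and the synopsis make the same split (new events "during which spontaneously reported new AEs/serious AEs (SAEs) will be recorded", active follow-up for ongoing ones) but mention no call.

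On questioning, Section 8.2.2 schedules an AE query "at the screening visit and throughout the confinement period and prior to being released from" confinement. Section 8.2.1 describes the method: "AEs should be collected mainly via face-to-face interview with the subject through spontaneous reporting or by the use of consistent, open, non-directive questions". Appendix A ticks AE recording in the Follow-Up column (D3) and specifies neither a contact nor a question.

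**The concern.** The follow-up has one stated purpose, which is to detect procedure-related events once participants have gone home. The method given for that period does not look for them. While participants are in the clinic they are asked about AEs; after release, the text waits for them to report. The scraping is done just before that change, on every participant and in both nostrils.

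Safety monitoring is a secondary objective. The AE tables would combine events found by questioning in the clinic with events found only by volunteering afterwards. A low post-discharge count could then reflect either few events or few reports, and the data could not tell the two apart.

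**Working it through.** The plan gives no figure on this point, so the check sets the passages side by side.

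**1. When scraping happens.** Sections 4.1 and 9.2 put T0 at 8 am ± 30 minutes and allow the last STT test from 12 h to 12 h 30 min after T0. Appendix A places scraping after that test.
- Earliest start of the last STT test: 07:30 + 12 h = 19:30.
- Latest start: 08:30 + 12 h 30 min = 21:00.
- A test may run 60 minutes (Section 7.2.8.7), so the latest finish is 22:00.

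Scraping is therefore an evening procedure on D2. Discharge belongs to the same visit, and follow-up is on D3. No interval between scraping and discharge is stated.

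**2. What contact each stage provides.**

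| Stage | Solicited AE contact in the text | Source |
|---|---|---|
| Screening and confinement | AE queries with non-leading questions | 8.2.2 |
| Before release | AE query (order relative to scraping not stated); brief physical examination after scraping | 8.2.2, 4.1 |
| After discharge, AE ongoing | Phone call from the site | 9.3 |
| After discharge, no AE ongoing | None stated | 9.3, 4.1, synopsis, 8.2.2 |

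**3. Whether another passage fills the last row.**
- The D3 tick in Appendix A is satisfied by writing down whatever is volunteered.
- Section 8.2.1 relies mainly on face-to-face interviews, and no visit follows discharge.
- Section 11.2 has AEs captured to the end of follow-up but does not say how they are to be found.

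None of these requires a question to every participant.

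**4. How many are affected.** The number without solicited contact after discharge is 14 minus those who leave with an ongoing AE. Its upper limit is 14 − 0 = 14.

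**5. Direction of the effect, under assumed values only.** Let p be the true proportion with a post-discharge event and s the share of events that come to light. The chance of recording at least one event among 14 is 1 − (1 − p·s)^14. Neither p nor s is in the documents.

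| p (assumed) | s = 1 | s = 0.5 | s = 0.25 |
|---|---|---|---|
| 5% | 51.2% | 29.8% | 16.1% |
| 10% | 77.1% | 51.2% | 29.8% |
| 20% | 95.6% | 77.1% | 51.2% |

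For example, with p = 10% and s = 0.5: 1 − 0.95^14 = 0.512. The table shows that incomplete reporting lowers the chance of seeing any event; it does not estimate by how much in this study.

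**The case against.** The strongest defence is proportionality. Section 2.3.2 also judges the procedure risks to be comparable with those of routine health examinations. The study is small and has no safety hypothesis, and passive reporting for one day is stated openly and consistently in three places. The word used there is monitoring, which does not promise questioning. This stands as a reason to treat the matter as a modest improvement. It does not explain how participants without an AE are to be monitored.

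A second defence is that the call may be meant for everyone: Section 9.3 directs it to the study participant without qualification, and the D3 tick is not limited to those with ongoing AEs. That is possible, but the sentence makes the call the means of following up ongoing events, and no question for it is given. The same edit is needed under either reading.

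A reader might infer more than the documents support:
- *No solicited contact after scraping.* The brief physical examination follows scraping, and the pre-release query may do so too. The gap begins at discharge.
- *Most scraping events would appear after discharge.* The documents give no onset times.
- *A comparison of the two scraping methods would be biased.* SAP Section 5.5.4.2 and Tables A 11 and A 12 present AEs by smoking group. No comparison by method is planned, and four participants receive both methods, one per nostril.

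**Conclusion.** The concern holds for events that start after discharge. The 1-day period is justified by procedure risk, yet as written a participant who leaves without an AE has no solicited contact in it. Up to all 14 participants could be in that position. Post-discharge events may therefore be under-counted in the overall AE summaries by smoking group. How many cannot be derived from the documents, because neither the event rate nor the share volunteered is given.

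The conclusion rests on reading the Section 9.3 call as limited to ongoing AEs, which is the more natural reading, and on taking Section 8.2.2 as the complete schedule of AE queries.

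One related point bears on what is caught before release. Section 7.2.5 lists a nasal and throat examination at discharge, while Appendix A shows it only at Visits 1 and 2. These need to be reconciled.

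**What to change.** State in Sections 9.3, 8.2.2 and 4.1 and in the synopsis that the site phones every participant on D3 and asks the open, non-directive AE question already given in Section 8.2.1, in addition to following up ongoing AEs. Mark this call in the D3 cell of the AE row in Appendix A. Section 8.2.2 must be included because it schedules the AE queries; leaving it unchanged would create a new inconsistency.

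The cost is at most 14 short calls by existing site staff and a sentence in each of the sections named. A few more minor AEs may be recorded.
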